Sample size calculations for visual acuity and vision scores were carried out separately using one-sided, one-sample mean t-test, with a type I error rate of 5% for each hypothesis. The hypothesis regarding visual acuity was powered to 99%, while the hypothesis for CLUE Vision scores was powered to 91%. Sample size calculations were performed using the *One-Sample T-Tests for Superiority by a Margin* procedure in Power Analysis & Sample Size (PASS2021) software Version 21.0.6 (NCSS LLC, Kaysville UT).⁹ Table 9 below, displays sample size estimates by endpoint.

Toric lens orientation and rotational stability

Sample size estimates for toric lens orientation and rotational stability were calculated using the same technique. Both endpoints are testing against an 80% threshold and have an event rate greater than 97%. A reference rate of 97.5% was used for toric lens orientation, while a worst-case scenario of 98% was used for rotational stability.

Toric lens orientation and rotational stability will be converted to a binary response as $YY = 1$ if a subject eye has absolute toric lens orientation $\leq 10^\circ$ (rotational stability: $Y=1$ if a subject eye has lens stability with blinks $\leq 5^\circ$) and $YY = 0$ otherwise, for analysis purposes. As indicated historical data of these products there was an extremely high rate ($> 97\%$) for both toric lens orientation and rotational stability for the test lens. Assuming a correlation of 0.70 between left and right eyes within the same subject, a total of 5000 replicating trials were simulated with a reference rate of 97.5% for toric rotation and 98% for rotation stability (worse-case scenario). Given the rare event binary outcome of $Y=0$, each replicated sample was analyzed using a Bayesian beta-binomial model with correlated binary data (Diniz et al; 2010).⁸ For each simulated trial, the upper bound of the 95% central posterior credible interval constructed for the percentage of acceptable lens fittings for the test lens was compared to a margin of 80%. With the proposed sample size, at least 99% of the estimated 95% credible intervals had the lower bound above 80%.

Secondary Endpoint Sample Size Calculations:

Clinical Study Protocol
Johnson & Johnson Vision Care, Inc.

CLUE Handling and Comfort Scores

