14.4. Level of Statistical Significance

All co-primary safety, co-primary efficacy, and secondary hypotheses will be tested using a multibranch gate keeping strategy. Study hypotheses will be evaluated sequentially as follows:

Clinical Study Protocol

CR-6521, v 3.0

■

JJVC CONFIDENTIAL

Clinical Study Protocol
Johnson & Johnson Vision Care, Inc.

First, co-primary safety hypotheses will be evaluated using 95% central posterior credible intervals for the probability of grade 3 or higher SLFs and acceptable lens fitting. Both hypotheses must be met in order to test co-primary efficacy hypotheses. Each co-primary efficacy hypothesis will be tested with a type I error rate of 5%. All co-primary safety and co-primary efficacy hypotheses must be met to test any secondary hypotheses. Secondary hypotheses will be tested utilizing a Bonferroni adjustment¹⁰ with an overall two-sided family-wise type I error rate of 5% (2.5% individually).

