Toric Lens Orientation and Rotational Stability at Least 15- Minutes Following Lens Settling

Absolute toric lens orientation (degrees) will be dichotomized as $Y=1$ if the absolute lens orientation (degrees) $\leq 10^\circ$ and $Y=0$, otherwise. Rotational stability will be quantified by lens stability with blinks (degrees). Lens stability will be dichotomized as $Z=1$ if the lens stability with blinks (degrees) $\leq 5^\circ$ and $Z=0$, otherwise.

Y and Z will be analyzed separately using a generalized linear mixed model with a binary distribution and the logit as the link function. Sequence of lens wear, lens type and period will be included in the model as fixed effects. Subject characteristics such as, gender, age and/or cylinder power may be included in the model if appropriate. Site ID and subject nested within site will be included in the model as random effects (G-side). The residual error between measurements within the same subject across study period will be modeled using an unstructured (UN) covariance structure. If the model fails to converge with a UN covariance, then a compound systemic (CS) covariance structure will be used. The Kenward and Roger Method will be used for the denominator degrees of freedom.¹¹

Primary Efficacy Hypothesis 2:

The null and alternative hypothesis to test for superiority of absolute lens orientation $\leq 10^\circ$ for the test lens relative to the threshold 80% are as follows:

$$\begin{aligned} H_{H_0}: pp_{TTTTTTTT} &\leq 80\% \\ H_{H_A}: pp_{TTTTTTTT} &> 80\% \end{aligned}$$

Where $pp_{TTTTTTTT}$, represents the population percentage for the percentage of eyes wearing the test lens with absolute lens orientation $\leq 10^\circ$. Superiority will be declared if the lower limit of the 95% CI is above 80.

Depending on the observed response rates for the percentage of subjects' eyes with absolute lens orientation $\leq 10^\circ$ and the percentage of subjects' eyes with lens stability with blinks $\leq 5^\circ$, a Bayesian hierarchical model accounting for zero event problem may be considered (i.e., 0% of eyes with toric rotation $>10^\circ$ [or lens stability $>5^\circ$]) . Details of this model will be provided in the stand-alone SAP.

Primary Efficacy Hypothesis 3:

The null and alternative hypothesis to test for superiority of lens stability with blinks $\leq 5^\circ$ for the test lens relative to the threshold 80% are as follows:

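### The logit mixed model for the two toric co-primaries gives no usable test-lens limit when the test lens has no failing eye in exactly one of its two periods, and the stated fallbacks do not cover that case.

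*Combined protocol and SAP*

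**What the plan says.** Section 14.5 of the combined protocol and SAP sets the model for both toric endpoints, orientation (Y) and stability (Z): "Y and Z will be analyzed separately using a generalized linear mixed model with a binary distribution and the logit as the link function". For the fixed part, "Sequence of lens wear, lens type and period will be included in the model as fixed effects". Site and subject within site are random. The decision rule for each endpoint is "Superiority will be declared if the lower limit of the 95% CI is above 80", and section 14.4 adds "Each co-primary efficacy hypothesis will be tested with a type I error rate of 5" percent. All co-primary hypotheses must be met.

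Three provisions could apply when the model misbehaves:

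- Covariance (14.5): "If the model fails to converge with a UN covariance, then a compound systemic (CS) covariance structure will be used".
- Zero events (14.5): depending on the observed rates, "a Bayesian hierarchical model accounting for zero event problem may be considered (i.e., 0% of eyes with toric rotation" above 10 degrees, or the stability equivalent. Details are left to a stand-alone SAP.
- Carryover (4.2): if a sequence effect is seen, the test uses first-period data.

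The sizing in 14.2 used another model: "each replicated sample was analyzed using a Bayesian beta-binomial model with correlated binary data". Table 9 reports 99% power for both endpoints on that basis.

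**The concern.** Success rates near 98% leave only a handful of failing eyes, and the model divides them over four lens-by-period cells. A cell without failures has an unbounded logit. If that cell belongs to the test lens, the quantity compared with 80% is undefined, although the lens may have succeeded in about 99% of eyes.

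At stake are two co-primary endpoints. A lens that clearly meets the threshold could be left without a valid limit because its few failures fell in one period. The analyst would then have to choose a rescue model that the protocol text does not fix. The stated power also describes an analysis that 14.5 does not plan for these endpoints.

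**Working it through.** **Inputs.** Success rates of 97.5% (orientation) and 98% (stability) and between-eye correlation ρ = 0.70, all from 14.2. 165 completers from 4.3. A 1:1 split (82 and 83 subjects) is my assumption; 5.1 says only that each block contains both sequences.

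**1. The plan's own figure.** In 5,000 trials simulated from the correlated-binomial mixture and analysed with the plan's Bayesian model, the share with a lower bound above 80% was 99.5% at n = 40, p = 0.975, and 100% at n = 100, p = 0.98. Table 9's 99% is reproduced, for that model.

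**2. Structure.** Intercept, sequence, lens and period make four parameters for four cells (design rank 4). The test-lens LS mean puts weights 0.5, 0, 0, 0.5 on the cells: it is the plain average of the two test-lens cell logits.

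**3. What happens with one test cell empty.** Test-lens failures were set at 5 of 164 eyes in one period and 0 of 166 in the other. In the fixed-effects fit:

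| Iterations | LS mean (logit) | SE | 95% CI for success |
|---|---|---|---|
| 5 | 5.01 | 0.7 | 97.6% to 99.8% |
| 10 | 7.51 | 7.6 | 0.06% to 100% |
| 25 | 15.01 | 13,820 | 0% to 100% |

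The printed limit depends on where the software stops. A random subject intercept does not help: in a one-test-cell-empty example the profile log-likelihood kept rising (-53.93, -44.93, -44.257) as the empty cell's logit went through 4, 10 and 25. With only a control cell empty, the fixed-effects test LS mean stayed at 3.58 (97.3%).

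**4. How often.** P(no failing eye among n subjects) = z = [(1-ρ)p² + ρp]^n. The two test cells hold different subjects, so P(exactly one empty) = 2z(1-z). With n = 82.5:

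- Orientation: 0.3 × 0.975² + 0.7 × 0.975 = 0.96769; z = 0.067; 2z(1-z) = 12.4%.
- Stability: 0.3 × 0.98² + 0.7 × 0.98 = 0.97412; z = 0.115; 2z(1-z) = 20.4%.
- At least one endpoint, if independent: 1 - 0.876 × 0.796 = 30%.
- Both test cells empty (z²), the event the fallback names: 0.4% and 1.3%.

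| Scenario | Orientation | Stability |
|---|---|---|
| 165 completers, ρ = 0.70 | 12.4% | 20.4% |
| 165 completers, ρ = 0 | 3.0% | 6.9% |
| 144 completers (minimum in 14.2), ρ = 0.70 | 17.0% | 25.7% |

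If true success were 99% or 99.5%, the chance at 165 and ρ = 0.70 would be 44.9% or 48.6%. At Table 9's own sample sizes (40 and 100) it would be 49.9% and 39.4%, so the 99% cannot be a property of the mixed model.

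**5. Effect on power, if a limit that cannot be estimated counts as not met.** The caps are 1 - 0.124 = 87.6% and 1 - 0.204 = 79.6%. The plan's combined figure is 0.99² × 0.99³ × 0.91 = 0.865.

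- Orientation loss only: 0.865 × 0.876 = 0.76.
- Both losses, independent: 0.865 × 0.876 × 0.796 = 0.60. If each cap replaces the 0.99 instead of multiplying it, this is 0.62; call it about 61%.

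**6. The alternative on the same kind of data.** The plan's correlated-binomial model on pooled test-lens data (162 subjects with both eyes passing, 1 with one failing eye, 2 with both failing; 5 failing eyes) gives a lower 95% bound of 96.4%.

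**The case against.** The strongest objection concerns stability. Step 1.21 in 7.2 discontinues a subject whose lens moves more than 5 degrees with blink, the same cut-off as the endpoint. The per-protocol set in 14.3 requires all visits, and Table 8 summarises efficacy on that set. Section 14.5 names a population only for safety. In a completers-only set stability failures largely vanish, both test cells are empty, and the named zero-event model would be available. This stands: the 20% figure depends on keeping the discontinued subjects. It does not rescue orientation, because rotation between 10 and 20 degrees does not end participation.

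Second, the zero-event sentence opens by referring to observed rates and does not say that the zero must be across both periods. The stand-alone SAP, due before database lock under 14.1, may widen it, and 14.10 allows documented changes. This also stands in part: it is not established that any rescue would be chosen after seeing the data. But the only trigger in the text is 0% of eyes failing, and its use is optional.

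Third, the defect can block a claim but hardly create a false one. That bears on severity.

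A reader might infer that the model will probably fail, or that any failure-free period breaks it. The figures do not support the first at the planning rates. The second is wrong, because control cells carry no weight in the test-lens mean. Nor does Table 8's 100% for stability make matters worse: at exactly 100% both test cells are empty, which is the case the fallback names.

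**Conclusion.** The point holds. Under 14.5 as written, a test lens with no failing eye in exactly one of its two periods has no finite LS mean and no usable 95% interval. Changing the covariance structure does not cure separation, the first-period rule addresses carryover, and the Bayesian option is discretionary with a different stated trigger.

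The risk is material but below even odds: about 12% for orientation and 20% for stability, and about 30% for at least one if independent. This assumes 165 completers, 1:1 allocation, ρ = 0.70 and, for stability, an analysis set that keeps discontinued subjects. It falls to about 3% and 7% without eye correlation, and reaches 45 to 49% only at success rates of 99 to 99.5%, which the plan does not state for these endpoints.

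It would be too strong to say that the trial's combined power is 61%. That needs a limit that cannot be estimated to count as failed (the plan does not say so), both endpoints to be affected, and independence. With the orientation loss alone it is about 76%. What is firm is that Table 9's 99% belongs to the beta-binomial model and not to the planned analysis. Severity: should be fixed.

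**What to change.** In 14.5, make the correlated beta-binomial model used for sizing the primary analysis for Efficacy Hypotheses 2 and 3. Apply it to the test-lens proportion, with the zero-event version already foreseen when no eye fails. Keep the sequence and period mixed model as a sensitivity analysis, and name it as the place where the sequence effect in 4.2 is assessed; otherwise that rule loses its trigger for these endpoints.

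At minimum, make the zero-event fallback mandatory and set its trigger to no failing eyes for the test lens in one or both periods.

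In either case, state the analysis population for the toric endpoints and how subjects discontinued at the toric fit step are counted.

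The cost is wording in the protocol and SAP, and the loss of sequence and period adjustment in the primary estimate. Under the first option, Table 9 would describe the analysis actually planned for these two endpoints.

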$$\begin{aligned} H_{H_0}: pp_{TTTTTTTT} &\leq 80\% \\ H_{H_A}: pp_{TTTTTTTT} &> 80\% \end{aligned}$$

Where $pp_{TTTTTTTT}$, represents the population percentage for the percentage of eyes wearing the test lens with lens stability with blinks $\leq 5^\circ$. Superiority will be declared if the lower limit of the 95% CI is above 80.

CLUE Vision Scores

CLUE vision scores after 1 week of lens wear will be analyzed using a linear mixed model adjusting for baseline scores as a covariate. Sequence of lens wear, lens type and period will be included in the model as fixed effects. Subject characteristics such as, gender, age and/or cylinder power may be included in the model if appropriate. Site ID will be included in the model as a random effect (G-side). The residual error between measurements within the same subject will be modeled using an unstructured (UN) covariance structure. If the model fails to converge with a UN covariance, then a compound systemic (CS) covariance structure will be used. The Kenward and Roger Method will be used for the denominator degrees of freedom.¹¹ CLUE Vision Scores estimates for each study lens will be estimated using 95% confidence intervals (CI) constructed for the least-square means (LSM).

Clinical Study Protocol
Johnson & Johnson Vision Care, Inc.

Primary Efficacy Hypothesis 4:

The null and alternative hypothesis to test for superiority of CLUE vision score for the test lens relative to the threshold 62 are as follows:

$$\begin{aligned} H_0: \mu_{TTTTTTTT} &\leq 62 \\ H_A: \mu_{TTTTTTTT} &> 62 \end{aligned}$$

Where $\mu_{TTTTTTTT}$, represents the population mean for test lens after 1 week of lens wear with respect to CLUE vision scores. Superiority will be declared if the lower limit of the 95% CI is above 62.

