14.6. Secondary Analysis

CLUE Handling and Comfort Scores

CLUE Handling and Comfort scores after 1-week of lens wear will be analyzed separately using a linear mixed model adjusting for baseline scores as a covariate. Sequence of lens wear, lens type and period will be included in the model as fixed effects. Subject characteristics such as, gender, age and/or cylinder power made be included in the model if appropriate. Site ID will be included in the model as a random effect (G-side). The residual error between measurements within the same subject will be modeled using an unstructured (UN) covariance structure. If the model fails to converge with a UN covariance, then a compound systemic (CS) covariance structure will be used. The Kenward and Roger Method will be used for the denominator degrees of freedom.¹¹ CLUE Handling and Comfort scores for each study lens will be estimated using 97.5% confidence intervals (CI) constructed for the least-square means (LSM).

Secondary Hypothesis 1:

The null and alternative hypothesis to test for superiority of CLUE Handling score for the test lens relative to the threshold 61 are as follows:

$$\begin{aligned} H_0: \mu_{TTTTTTTT} &\leq 61 \\ H_A: \mu_{TTTTTTTT} &> 61 \end{aligned}$$

Where $\mu_{TTTTTTTT}$, represents the population mean for test lens after 1 week of lens wear with respect to CLUE Handling scores. Superiority will be declared if the lower limit of the 97.5% CI is above 61.

Secondary Hypothesis 2:

The null and alternative hypothesis to test for superiority of CLUE Comfort score for the test lens relative to the threshold 58 are as follows:

$$\begin{aligned} H_0: \mu_{TTTTTTTT} &\leq 58 \\ H_A: \mu_{TTTTTTTT} &> 58 \end{aligned}$$

Where $\mu_{TTTTTTTT}$, represents the population mean for test lens after 1 week of lens wear with respect to CLUE comfort scores. Superiority will be declared if the lower limit of the 97.5% CI is above 58.

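### CLUE threshold tests: a baseline-adjusted LS-mean interval taken at the sample-average baseline omits baseline sampling variance, and the stated error levels conflict

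*Combined protocol and SAP*

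**What the plan says.** Section 14.5 states for CLUE Vision: "CLUE vision scores after 1 week of lens wear will be analyzed using a linear mixed model adjusting for baseline scores as a covariate". Sequence, lens and period are fixed effects, site is random, the within-subject covariance is unstructured, and degrees of freedom are Kenward-Roger. The parameter in Primary Efficacy Hypothesis 4 "represents the population mean for test lens after 1 week of lens wear with respect to CLUE vision scores". The decision rule is "Superiority will be declared if the lower limit of the 95% CI is above 62", applied to the LS-mean interval. In section 14.6, Handling and Comfort "will be analyzed separately using a linear mixed model adjusting for baseline scores as a covariate", and the lower 97.5% limits are compared with 61 and 58.

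The baseline score comes from one questionnaire at Visit 1 about the subject's habitual lenses (section 7.2, step 1.8). The documents do not give the baseline value at which the LS means are taken. Section 14.1 leaves further detail to a stand-alone SAP that is not among them.

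The error level is described in several ways:

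- **Vision.** The introduction to 14.2 gives two-sided 5%. The Vision paragraph of 14.2 gives one-sided 5%. Section 14.4 gives 5% without saying how many sides. The 95% limit in 14.5 amounts to one-sided 2.5%.
- **Handling and Comfort.** Section 14.2 gives one-sided 2.5% each. Section 14.4 gives two-sided 2.5% each. The 97.5% interval in 14.6 amounts to one-sided 1.25%.

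**The concern.** These are single-lens comparisons with a fixed score, not contrasts between lenses. In a contrast the baseline term largely cancels. In a single mean it does not: the estimate carries the sampling error of the average baseline.

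At the sample-average baseline, adjustment hardly moves the test-lens mean when every subject wears both lenses. It does remove the variance explained by baseline from the standard error. Kenward-Roger allows for estimated covariance parameters but still treats covariates as fixed, so it does not put that variance back. The interval then suits a mean at a given baseline, not the population mean in the hypothesis.

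CLUE Vision is the co-primary with the least power (91%, against 99% for the others in Table 9), and every co-primary must pass. If the interval is too short, a lens whose true mean equals the threshold passes more often than the stated confidence implies. The conflicting error levels add to this, because the excess can only be judged against a settled level.

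**Working it through.** **1. Reproduce the plan's power.** Inputs: mean 67.4 and SD 19.67 (Table 8), threshold 62, n = 144 (Table 9). The difference is 67.4 − 62 = 5.4, the standard error is 19.67/√144 = 1.639, and the noncentrality is 5.4/1.639 = 3.29. Noncentral-t power of the one-sample t-test:

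- one-sided 2.5%: 90.5%, which rounds to the stated 91%
- one-sided 5%: 94.9%; about 120 subjects would be enough for 91%

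The stated figure therefore belongs to one-sided 2.5%.

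**2. The missing term.** Let r be the correlation of baseline with the 1-week score (assumed; not in the documents). Ignoring sites:

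- model-based variance at the sample-average baseline: SD²(1 − r²)/N
- omitted: slope² × Var(baseline)/N = r²SD²/N
- sum: SD²/N, the actual variance of the estimate
- one-sided error of the 95% limit: 1 − Φ(1.96√(1 − r²))

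At N = 165 and r = 0.5, the model SE is 19.67 × 0.866/√165 = 1.326. The omitted variance is 0.25 × 19.67²/165 = 0.586, and √(1.326² + 0.586) = 1.531 = 19.67/√165. The formula gives 3.1%, 4.5% and 5.8% at r = 0.3, 0.5 and 0.6.

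**3. The planned model.** Simulated with 165 subjects, 14 random sites, two periods, unstructured covariance, REML, Kenward-Roger, and the LS mean at the sample-average baseline. Assumed: within-subject correlation 0.5, complete data, site ICC 0, 0.02 or 0.05. The true mean is at the threshold. There were 20,000 trials per cell, with a Monte Carlo error of about 0.1 points. One-sided error by ICC 0 / 0.02 / 0.05:

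| r | 95% limit (implied 2.5%) | 97.5% limit (implied 1.25%) |
|---|---|---|
| 0.3 | 2.43 / 2.72 / 2.74% | 1.21 / 1.29 / 1.35% |
| 0.5 | 3.67 / 3.74 / 3.55% | 1.96 / 2.13 / 1.85% |
| 0.6 | 4.87 / 4.73 / 4.08% | 2.94 / 2.78 / 2.37% |

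Without the covariate the rates are 1.92-2.50% and 0.86-1.31%. The site term alone thus makes the interval slightly conservative in places and partly offsets the shortfall, which is why these figures lie below step 2. With the missing variance added, the 95% limit gives 1.93-2.38%. For the 97.5% limit, the added term was checked only without sites, at 144 subjects: 1.2-1.3%.

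At r = 0.5 and ICC 0.02 the adjusted SE averages 1.51, while the estimate's actual SD is 1.69. The adjusted and unadjusted estimates there never differ by more than 0.11 points.

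**4. First-period-only rule.** Section 4.2 restricts the primary test to period 1 if a sequence effect is seen. Take 83 test-lens and 82 control subjects, r = 0.5, no site effect:

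- unadjusted SD: 19.67/√83 = 2.16
- adjusted, residual part: 19.67² × 0.75/83 = 3.50
- adjusted, omitted part: 0.586, as in step 2
- adjusted, actual SD: √(3.50 + 0.586) = 2.02

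In simulation the adjusted interval as planned has 3.5% one-sided error. With the added term it has 2.5%.

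**5. Secondary levels.** The stated 97% power does not identify the intended level. At n = 135 the plan's t-test gives Handling (difference 4.4, SD 21.50) 65.6% at one-sided 2.5% and 54.5% at 1.25%. Comfort exceeds 99% at both.

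**The case against.** The best defence is that the harm rests on a correlation that the documents do not give. The baseline rates a different product, the subject's own lenses, so 0.5 or 0.6 cannot be presumed, and at 0.3 the planned model shows no material excess. This stands. A reader might infer that the co-primary error rate is inflated as planned. The documents do not support that: the excess needs both a correlation of about 0.5 or more and evaluation at the sample average.

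A second defence is that none of the Vision rates in step 3 exceeds the one-sided 5% in the Vision paragraph of 14.2. The secondary rates likewise stay within one-sided 2.5% up to correlation 0.5. That is correct arithmetic. But the decision rules in 14.5 and 14.6 are the stricter ones, and for Vision the stated power agrees with the stricter level.

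Third, the stand-alone SAP could state the evaluation point. It could, but naming the sample average would not by itself correct the standard error. A fixed, pre-stated baseline would make the interval valid, but for the mean at that baseline, not for the population mean in the hypothesis.

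A reader might also extend the point to the sentence "Subject characteristics such as, gender, age and/or cylinder power may be included in the model if appropriate". Their inclusion is conditional, the documents give no correlation with the score, and no effect was calculated, so nothing is claimed about them.

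**Conclusion.** The concern holds conditionally. If the LS means are taken at the sample-average baseline, the three CLUE intervals omit a real part of the variance of the population-mean estimate. For Vision, the one-sided error against 2.5% is about 2.4-2.7% at correlation 0.3, 3.6-3.7% at 0.5 and 4.1-4.9% at 0.6. For Handling and Comfort, against 1.25%, it is 1.2-1.4%, 1.9-2.1% and 2.4-2.9%. These figures rest on the assumed correlations, site ICCs of 0-0.05, 14 sites and complete data.

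The error-level conflict needs no assumption about the covariate. The one-sided 5% in the Vision paragraph of 14.2 is wrong as written. For the secondaries, 14.2 conflicts with 14.4 and 14.6.

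A reader might conclude that the covariate should be removed. The documents point the other way: under the first-period-only rule of 4.2, adjustment brings a real gain in precision (SD 2.02 against 2.16 at correlation 0.5).

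**What to change.** 1. In 14.5 and 14.6, or in the stand-alone SAP, keep the baseline covariate and state that the LS mean is taken at the sample-average baseline. For the three threshold tests, add slope² × baseline variance / N to the LS-mean variance, where N is the number of subjects in that average. This works for both the two-period and the first-period-only analysis.

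2. In 14.2, change the Vision level from one-sided 5% to one-sided 2.5%. Reconcile the one-sided 2.5% for Handling and Comfort with the 97.5% intervals in 14.6, and state the number of sides wherever a level appears.

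Both are changes of wording, with no new data. The first widens the intervals: ignoring sites, by 1/√(1 − r²), about 5%, 15% and 25% at correlations 0.3, 0.5 and 0.6. At 165 subjects and correlation 0.5, apparent Vision power falls from 95.4%, 90.7% and 81.9% to 92.4%, 86.7% and 77.5% at site ICC 0, 0.02 and 0.05, a loss of 3.0 to 4.4 points. Part of the higher figures came from the understated standard error. Where power falls below the 90% minimum in 14.2, the main cause is site variance, which the sizing t-test leaves out.
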